## ***2.5. Conditions of the trial***

This clinical trial will be conducted in accordance with this protocol, the principles of the World Medical Association Declaration of Helsinki, the ICH Good Clinical Practice (ICH GCP) standard, and Russian law:

1. Federal Law dated 12 April 2010 N 61-FZ "On Circulation of Medicines" (in the current version);
2. National Standard of the Russian Federation GOST R 52379-2005 "Good Clinical Practice";
3. Order of the Ministry of Health of the Russian Federation No. 200n dated 01 April 2016 "On Approval of the Rules of Good Clinical Practice";
4. Resolution of the Government of the Russian Federation dated 13 September 2010 N 714 "On Approval of Model Rules for Compulsory Life and Health Insurance of a Patient Participating in Clinical Trials of a Medicinal Product" (current version);
5. Order of the Ministry of Health of the Russian Federation No. 986n of 29 November 2012 "On Approval of the Regulations on the Ethics Council";
6. Decision of the Council of the Eurasian Economic Commission of 03.11.2016 No. 79 "On Approval of the Rules of Good Clinical Practice of the Eurasian Economic Union".

## ***2.6. Description of the trial population***

Outpatients - boys and girls, aged 6 to 12 years (inclusive) with a diagnosis of attention deficit hyperactivity disorder, established in accordance with the criteria of the 10th revision of the International Classification of Diseases (ICD-10) (F90.0) and the Diagnostic and Statistical Manual of Mental Disorders 5th edition (DSM-5) by a psychiatrist or neurologist.

### **3. TRIAL AIMS AND OBJECTIVES**

#### ***3.1. Trial aims***

To evaluate the efficacy and safety of two dosing regimes of Mexidol® film-coated tablets, 125 mg (PRC Pharmasoft LLC, Russia) vs. placebo in children aged 6 to 12 years inclusive with attention deficit hyperactivity disorder (ADHD).

#### ***3.2. Trial objectives***

##### **Primary objective:**

1. To evaluate the efficacy of Mexidol® film-coated tablets, 125 mg (PRC PHARMASOFT LLC, Russia) vs. placebo after 6 weeks from the beginning of therapy in relation to the average change in the total score on the "inattention" and "hyperactivity/impulsivity" subscales of the SNAP-IV scale when administered at a dose of 125 mg OD.
2. To evaluate the efficacy of Mexidol® film-coated tablets, 125 mg (PRC PHARMASOFT LLC, Russia) vs. placebo after 6 weeks from the beginning of therapy in relation to the mean change in the total score on the "inattention", "hyperactivity/impulsivity" subscales of the SNAP-IV scale when administered at a dose of 125 mg BID.

##### **Secondary objectives:**

1. To evaluate the efficacy of Mexidol® film-coated tablets 125 mg (PRC PHARMASOFT LLC, Russia) vs. placebo after 6 weeks from the beginning of therapy when administered at a dose of 125 mg OD and 125 mg BID on the basis of the following parameters:
  - a. mean change on the SNAP-IV subscale - inattention;
  - b. mean change on SNAP-IV subscale - hyperactivity/impulsivity
  - c. mean change on the SNAP-IV subscale - oppositional defiant disorder;
  - d. mean change on the SNAP-IV subscale - Conners' clinical index;
  - e. mean change on the Spence Children's Anxiety Scale (SCAS);
  - f. mean change on ADHD Rating Scale-IV value;
  - g. Clinical Global Impressions-ADHD-Severity scale (CGI-ADHD-S);
  - h. assessment of the dynamics of PedMIDAS questionnaire scores (number of days with restriction of daily activity due to headache, number of days with headache, average headache severity and maximum headache severity in scores);
  - i. Clinical Global Impressions Scale - Improvement (CGI-I).
2. To evaluate the safety of Mexidol® film-coated tablets, 125 mg (RPC PHARMASOFT LLC, Russia) vs. placebo based on the assessment of frequency, severity and nature of adverse events.

### **4. TRIAL DESIGN**

#### ***4.1. Efficacy criteria***

Evaluation of the efficacy of therapy will be based on primary and secondary efficacy criteria.

CONFIDENTIAL

36

Protocol version 4.0 dated 15.10.2019.

**Primary efficacy criterion:**

1. Mean change in the total score on the inattention and hyperactivity/impulsivity subscales of the SNAP-IV scale after 6 weeks of therapy vs. baseline.

[figure not shown]
**Secondary efficacy criteria:**

1. mean change on the SNAP-IV inattention subscale after 6 weeks of therapy vs. baseline;
2. mean change on SNAP-IV subscale hyperactivity/impulsivity after 6 weeks of therapy vs. baseline;
3. mean change on the SNAP-IV subscale, oppositional defiant disorder, after 6 weeks of therapy vs. baseline;
4. mean change in SNAP-IV subscale - Conners index after 6 weeks of therapy vs. baseline;
5. mean change on the Spence children's anxiety scale (SCAS) after 6 weeks of therapy vs. baseline;
6. mean change on ADHD Rating Scale-IV scores after 6 weeks of therapy vs. baseline;
7. clinical Global Impressions-ADHD-Severity (CGI-ADHD-S) scale score after 6 weeks of therapy vs. baseline;
8. assessment of the dynamics of PedMIDAS questionnaire scores (number of days with restriction of daily activity due to headache, number of days with headache, average headache severity and maximum headache severity in scores);
9. Clinical Global Impressions Scale - Improvement (CGI-I) score after 6 weeks of therapy vs. baseline.

**4.2. *Trial design***

This trial is a multicentre, prospective, double-blind, randomised 1:1:1 clinical trial of the safety and efficacy of Mexidol® film-coated tablets 125 mg in three parallel groups using placebo control (Figure 1).

**Figure 1. Graphical design of the trial**

### ***4.3. Description of measures aimed at minimising/eliminating subjectivity***

#### ***4.3.1. Randomisation***

Patient randomisation will be performed at Visit 2 with a 1:1:1:1 patient allocation using the online IWRS (Interactive Web Response System). A patient randomisation number will be assigned to the trial subject in the order in which they access the IWRS system.

The corresponding randomisation list will be generated in the statistical software using a random number generator by the responsible biostatistician of the Sponsor/Sponsor's representative company. The randomisation list is not intended to be shared with research centres and will be held by the Sponsor. Due to the use of a centralised randomisation system, envelopes or other means of conducting randomisation will not be provided to centres.

Investigators will be given online training on how to use the IWRS system.

The randomisation list will be included in the Trial Master File and the final clinical trial report. A register of screened and randomised patients will be maintained for all sites. The register form is contained in the Investigator Site File. The form should be completed by the investigator on a regular basis with all necessary data entered.

The randomisation number is the unique code of the patient in the clinical trial. The investigator records the patient's randomisation number in the source documentation and electronic Case Report Form (eCRF) and enters the randomised patient's information in the list of included patients. The randomisation number cannot be changed during the course of the trial.

The prescribed therapy cannot be changed during the trial.

Patients who early terminate the trial will not be replaced.

Each patient will be assigned an individual identification number of the following form of three digits: \_\_\_\_\_ - \_\_\_\_\_ - \_\_\_\_\_ - \_\_\_\_\_, where the first two digits of the number correspond to the centre number, the next two digits denote the screening number within each clinical centre, the

last three digits of the number correspond to the randomisation number generated by the IWRS randomisation system.

#### 4.3.2. *Blinding*

The trial is double-blind, so neither the patient nor the investigator will be aware of the therapy group to which the patient will be randomised. To ensure a double-blind trial design, randomisation using the online IWRS system and appropriate labelling of the investigational products is provided.

As the trial will investigate 2 dosing regimens - taking 1 tablet OD (group 1) and 1 tablet BID (group 2), to maintain double-blinding of the prescribed therapy, patients in group 1 will take 1 tablet of placebo, 12±1 hours after taking the investigational product. Thus, for all groups, a 2-fold dosing regimen will be followed.

### 4.4. *Investigational products, dosages, routes of administration, packaging, labelling*

#### 4.4.1. *Information on Investigational Products*

##### Investigational Product

Name	Mexidol®
Group name:	Ethylmethylhydroxypyridine succinate
Dosage form	film-coated tablets
Composition:	Composition: Active substance: ethylmethylhydroxypyridine succinate (2-ethyl-6-methyl-3-hydroxypyridine succinate) - 125.0 mg Excipients: lactose monohydrate - 97.5 mg, povidone 25.0 mg, magnesium stearate - 2.50 mg. Film coating: opadry II white 33G28435 - 7.5 mg (hypromellose - 3.0 mg, titanium dioxide - 1.875 mg, lactose monohydrate - 1.575 mg, polyethylene glycol (macrogol) - 0.6 mg, triacetin - 0.45 mg)
Description:	round, biconvex, film-coated tablets, from white to white with creamy colour
Pharmacotherapeutic group	antioxidant agent
ATC Code:	N07XX

##### Placebo

Name of the drug	not applicable
INN:	not applicable
Dosage form	film-coated tablets
Composition:	Composition: lactose monohydrate - 222.5 mg, povidone 25.0 mg, magnesium stearate - 2.50 mg Film coating: opadry II white 33G28435 - 7.5 mg (hypromellose - 3.0 mg, titanium dioxide - 1.875 mg, lactose

	monohydrate - 1.575 mg, polyethylene glycol (macrogol) - 0.6 mg, triacetin - 0.45 mg)
Description:	round, biconvex, film-coated tablets, from white to white with a creamy tinge colour
Pharmacotherapeutic group	not applicable
ATC Code:	not applicable

#### **4.4.2. Production, packaging and labelling**

In accordance with the requirements of the Good Manufacturing Practice Rules (approved by Order of the Ministry of Industry and Trade of the Russian Federation No. 916 dated 14 June 2013; current version), the following information will be applied to the primary packaging of medicinal products for clinical trials:

- name of the medicinal product Mexidol® / placebo;
- Sponsor;
- pharmaceutical form, dosage and number of tablets in the package;
- number (code) of the trial;
- "For clinical trials";
- batch number;
- expiry date
- "Morning" or "Evening."

The following information will be labelled on the secondary packaging of the medicinal product for the clinical trial:

- sponsor's name and contact information;
- name and contact details of the manufacturer;
- name of the medicinal product Mexidol® / placebo;
- pharmaceutical form, dosage and number of tablets in the package;
- "If you experience any side effects, consult a doctor!";
- protocol number (code);
- directions for use;
- method of application;
- storage conditions;
- "Keep out of reach of children."
- "For clinical trials";
- "Morning" or "Evening";
- date of prescription;
- return date;
- patient identification information;
- patient's randomisation code;
- visit number;
- Full name of the investigator;
- batch number;
- date of manufacture;
- shelf life.

The following information will be labelled on the tertiary packaging of the medicinal product

for the clinical trial:

- sponsor's name and contact information;
- name and contact details of the manufacturer;
- name of the medicinal product Mexidol® / placebo;
- dosage form, dosage, number of packs and tablets in the pack;
- patient identification information;
- Full name of the investigator;
- protocol number (code);
- Full name of the investigator;
- patient's randomisation code;
- method of application;
- batch number;
- date of manufacture;
- shelf life;
- "If you experience any side effects, consult a doctor!";
- directions for use;
- storage conditions;
- "Keep out of reach of children."
- "For clinical trials".

The primary package will be a blister with 10 tablets. Five blisters will be enclosed in secondary packaging - 2 carton packs, each labelled "Morning" or "Evening" for the morning or evening dose respectively. Patients in all groups will therefore be given a set of two secondary packs contained in a single tertiary pack (carton pack).

#### ***4.4.3. Dosing in patients***

##### **Investigational product**

**Mexidol®** (ethylmethylhydroxypyridine succinate) film-coated tablets, 125 mg (RPC PHARMASOFT LLC, Russia).

##### ***Method of administration:***

In **Group 1** , the drug will be administered orally 1 tablet OD. Patients additionally take 1 placebo tablet. The interval between drug and placebo administration was  $12\pm1$  hours.

Duration of therapy: 42 days.

In **Group 2** , the drug will be administered orally 1 tablet BID. The interval between doses is  $12\pm1$  hours.

Duration of therapy: 42 days.

**Placebo** film-coated tablets (RPC PHARMASOFT LLC, Russia).

##### ***Method of administration:***

In **group 3**, placebo will be administered orally 1 tablet BID. The interval between doses is  $12\pm1$  hours.

Duration of therapy: 42 days.

#### ***4.5. Expected duration of patient participation in the trial, description of trial periods and procedures***

##### **4.5.1. Trial duration**

The duration of treatment is 42 days. The duration of the follow-up period is 7 days.

Screening and randomisation can be carried out on the same day provided all screening procedures are performed, and results are available.

The total minimum duration of patient participation in the trial will be 49 full days: a screening and therapy period of 42 days plus a follow-up period of 7 days.

The total maximum duration of patient participation in the trial will be 67 days: a screening period of 14 days plus a therapy period of 42 days plus a follow-up period of 7 days, plus a window for the end-of-therapy visit (Visit 5) of 1 day and the follow-up visit (Visit 6) of 3 days.

##### ***4.5.2. Beginning of the Trial. Visit 1 (Day -14 -1) Screening.***

The start of the trial will be the inclusion (screening) of the first patient in the trial. In the Russian Federation, in accordance with the Federal Law "On Circulation of Medicines", the head of a medical organisation (research centre) shall, within a period not exceeding three working days from the date of commencement of a clinical trial of a medicinal product for human use, notify the authorised federal executive body that issued the permit to conduct such a trial, in the form established by it.

Each potential research participant should be adequately informed about the aims, methods, expected benefits of the research and the risks and inconveniences associated with participation in the research.

Patients must be provided with comprehensive and accurate information regarding all aspects of the trial prior to any procedures and activities related to the trial. Prior to any procedures, the Patient Information Sheet with the Informed Consent Form (hereinafter referred to as Informed Consent) must be personally signed and dated by one of the patient's parents in 2 copies, thus confirming consent to the patient's participation in the trial, one of which is handed over to the patient's parent. Immediately after signing the Informed Consent, the patient/patient's parent will be issued an Insurance Policy for the patient participating in the clinical trial.

Next, an electronic Case Report Form (eCRF) is created for each patient, where all the necessary data is entered.

The patient's parents are cautioned about restrictions on the use of concomitant therapy during the trial. A list of prohibited medications is listed in the Patient Information Sheet.

In addition, parents will be given a handout with information on how to comply with the rules of patient participation in the trial, restrictions and how to complete the Patient Diary.

Once the Informed Consent is signed by one of the patient's parents, screening procedures are performed.

Screening confirms that the patient fulfils the trial eligibility criteria: fulfilment of all inclusion criteria and absence of all non-inclusion criteria.

The duration of screening can be up to 14 days before randomisation.

At the visit, the investigator records the diagnosis and the following procedures are performed:

- collection of demographic data and history;
- measurement of height, body weight, calculation of body mass index (BMI);
- assessment of inclusion/non-inclusion criteria;
- registration of concomitant and pre-existing pathology;
- registration of concomitant and prior therapy;
- physical examination with recording of BP, HR, and RR;
- Complete Blood Count;
- blood chemistry;
- urinalysis;
- neurological status;
- completion of the SNAP-IV scale by the investigator from the parents' words;
- CGI-ADHD-S scale score by the investigator.

The sum of the total score on the inattention, hyperactivity/impulsivity subscales of the SNAP-IV scale obtained at screening will be considered as the baseline against which the efficacy assessment planned in this protocol will be performed.

A date is set for the next visit (if necessary) or a randomisation visit (Visit 2) is conducted, provided all screening procedures have been completed and results of all tests have been obtained.

#### ***4.5.3. Visit 2 (Day 1). Randomization. Initiation of therapy.***

The following procedures are performed on Visit 2:

- registration of concomitant therapy;
- assessment of inclusion/non-inclusion criteria;
- evaluation of exclusion criteria;
- AEs registration;
- sNAP-IV and CGI-ADHD-S score if the interval between Visit 1 and Visit 2 is 7 or more days.

In this case, the value obtained at Visit 2 is taken as the initial value of the sum of scores on the "inattention" and "hyperactivity/impulsivity" subscales of the SNAP-IV scale, and this value is used in further calculations of performance indicators.

If the patient continues to meet all the criteria for trial participation, the randomization procedure and the following procedures are performed:

- SCAS score: to be completed by the investigator from the patient's parents
- ADHD Rating Scale IV: to be completed by the investigator from the patient's parents;
- completion of an examination card for a child/adolescent with headache (if the patient has complaints of headache, at Visit 2 it is completed for the previous 3 months);
- completion of the PedMIDAS questionnaire (if the patient has complaints of headache, at Visit 2 it is completed for the previous 3 months).

The drug is dispensed in a quantity sufficient to provide therapy until the date of the next visit. The scheme of administration of the drug is explained. A handout for parents, the Patient Diary and instructions on how to complete it are given. A date is set for the next visit. The patient is

warned to bring all unused medication in its original packaging and a completed Patient Diary to the next visit.

#### **4.5.4. Visit 3 (Day 14±2), telephone contact**

Visit 3 takes the form of a telephone contact by the investigator 14 days from the start of treatment with the patient's parents. It is necessary to obtain information from parents about the general tolerability of therapy, adverse events that have occurred since the last assessment, prescribed drugs of concomitant therapy, remind about compliance with the therapy regime. If necessary, an unscheduled visit to the clinical centre by the patient may be scheduled based on the information received, or a follow-up telephone contact may be scheduled at the discretion of the investigator to monitor adherence to recommendations.

#### **4.5.5. Visit 4 (Day 28±2), telephone contact**

Visit 4 takes the form of a telephone contact by the investigator 28 days from the start of treatment with the patient's parents. It is necessary to obtain information from parents about the general tolerability of therapy, adverse events that have occurred since the last evaluation, symptom scores according to the ADHD Rating Scale IV, concomitant medications prescribed, and remind them of compliance with therapy. If necessary, an unscheduled visit to the clinical site by the patient may be scheduled based on the information received, or a follow-up telephone contact may be scheduled at the discretion of the investigator to monitor adherence to recommendations.

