## 1.2. *Schedule of trial visits and procedures*

Procedures	Visits					
	Screening	Initiation of therapy	Telephone contact 	Telephone contact 	End of therapy	Follow-up
Day	-14-1	1	14±2	28±2	43±1	50±3
Visit number	1	2	3	4	5	6
Informed consent	X					
Demographic data and history	X					
Measurement of height, body weight, BMI calculation	X					
Registration of previous therapy	X					
Registration of previous pathology	X					
Registration of comorbidities	X					
Registration of concomitant therapy	X	X	X	X	X	X
Inclusion / non-inclusion criteria	X	X				
Exclusion criteria		X			X	
Physical examination with measurement of BP, HR, and RR	X				X	X
Complete Blood Count 	X				X	
Biochemical blood test 	X				X	

 During telephone contact, the investigator should obtain information about the general tolerability of treatment, the occurrence of AEs, prescribed concomitant medications, and remind about compliance with the therapy regimen

 During the telephone contact, the investigator should obtain information about general tolerability of treatment, occurrence of NSAIDs, prescribed concomitant medications, ADHD Rating Scale IV score, and remind about adherence to the therapy regimen

 Haemoglobin; haematocrit; red blood cell count; platelet count; white blood cell count and complete white blood cell count; ESR

 Total protein; albumin; glucose; ALT; AST; total bilirubin, alkaline phosphatase (ALP), amylase, creatinine

Procedures			Visits			Follow-up
			Therapy			
	Screening	Initiation of therapy	Telephone contact 	Telephone contact 	End of therapy	
Day	-14-1	1	14±2	28±2	43±1	50±3
Visit number	1	2	3	4	5	6
Clinical urinalysis 	X				X	
AE registration		X	X	X	X	X
Neurological status	X				X	X
SNAP-IV score	X	X			X	
Randomization		X				
SCAS score		X			X	
ADHD Rating Scale IV score		X		X	X	
CGI-ADHD-S score	X	X			X	
CGI-I score					X	
PedMIDAS questionnaire score 		X			X	
Completion of an assessment card for a child/adolescent with headache 		X			X	
Dispensing and/or record keeping of medications		X			X	
Assessment of adherence to therapy					X	

 Colour, transparency, pH, specific gravity, protein, glucose, leucocytes, red blood cells, bacteria, cylinders, salts

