#### **Secondary efficacy criteria:**

1. Mean change on the SNAP-IV inattention subscale after 6 weeks of therapy vs. baseline;
2. Mean change on SNAP-IV subscale hyperactivity/impulsivity after 6 weeks of therapy vs. baseline.
3. Mean change on the SNAP-IV subscale, oppositional defiant disorder, after 6 weeks of therapy vs. baseline.
4. Mean change in SNAP-IV subscale - Conners index after 6 weeks of therapy vs. baseline.
5. Mean change on the Spence children's anxiety scale (SCAS) after 6 weeks of therapy vs. baseline.
6. Mean change on ADHD Rating Scale-IV scores after 6 weeks of therapy vs. baseline.
7. Clinical Global Impressions-ADHD-Severity scale (CGI-ADHD-S).
8. assessment of the dynamics of PedMIDAS questionnaire scores (number of days with restriction of daily activity due to headache, number of days with headache, average headache severity and maximum headache severity in scores).
9. The Clinical Global Impressions Scale - Improvement (CGI-I) score.

At the moment there are no Russian regulatory recommendations for conducting clinical studies of medicinal products for ADHD, so the recommendations of the European Medicines Agency (EMA) are used as the main ones, according to which it is recommended to use rating scales as the main criterion for assessing efficacy.

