### **9.7. *Selection of data for statistical analysis***

Analyses will be conducted in the following populations:

- 1) safety population - will include all randomized patients who have taken at least one dose of the Investigational product;
- 2) the full analysis set (FAS) population will include all randomised patients who have taken at least one dose of Investigational product and who have an assessment of response to therapy after 6 weeks of therapy. This will be the main population for efficacy analyses;
- 3) PP (per protocol population) is a subgroup of the FAS population that will include patients in the absence of significant protocol deviations with respect to inclusion/exclusion criteria, adherence to therapy, and use of concomitant therapy. This will be an additional population used for efficacy analyses.

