### ***10.2. Deviations from protocol***

In general, any deviation from the protocol may be accepted only in an urgent case or after obtaining written agreement from the Sponsor and subject to approval by the Ethics Committee. Any deviation from the protocol should be clearly explained in the source documentation and in the eCRF. Classification of protocol deviations will be made before the database cutt off by the Sponsor's medical expert. Deviations from the protocol will be considered significant in the following cases (the list may be expanded in a subsequent evaluation of protocol deviations):

- skip of visit 5;
- violation of inclusion / non-inclusion criteria;
- violation of the exclusion criteria;
- taking the Investigational product/placebo <80% or >120% of the total number of tablets prescribed;
- administration of prohibited drugs.

If significant deviations from the protocol are identified, the CRA must immediately inform the Sponsor.

In the absence of data at Visit 5 when data are available at Visit 6, these patients will not be included in the FAS and PP populations, but will be analysed in the safety population.

In the presence of data at Visit 5 and the presence of the other listed significant protocol deviations, these patients will be included in the full analysis population, safety population, but excluded from the protocol population.

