- **Various assessments for treatment success:** secondary efficacy endpoints were planned to support the results of the primary efficacy analysis using the t-test - for data whose distribution conforms to the law of normal distribution, or the Mann-Whitney U-test for data whose distribution does not conform to the law of normal distribution.
- **Missing data:** analyses of full cases and post-hoc analyses using the last observation carry forward method (LOCF) to assess consistency of results are assumed.

The feasibility of using a number of statistical methods will be assessed after data collection has been completed, as the nature of the data distribution, sample homogeneity, etc. is not known in advance. During the course of the analysis, the list of methods to be used may be modified and supplemented if necessary for the qualitative processing of the data.

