## Plan for statistical analysis of efficacy and safety parameters

Table 4. Statistical analysis of secondary, endpoints (SNAP-GU, CGI-ADHD-S, SCAS, PedMIDAS and ADHD Rating Scale IV) (template)

Indicator 	Mexidol®				Placebo				Mexidol®+ Placebo			
	Visit 2 (Day 1)	Visit 5 (Day 43+1)	Dynamics		Visit 2 (Day 1)	Visit 5 (Day 43+1)	Dynamics		Visit 2 (Day 1)	Visit 5 (Day 43+1)	Dynamics	
			Abs.	%			Abs.	%			Abs.	%
N												
Mean												
95% CI, L												
95% CI, U												
Median												
Min												
Max												
Q 1												
Q 3												
Range												
QRange												
SD												
CV												
Intragroup comparison: comparison of data at the end of therapy with data at the start of therapy (statistical criterion  ) (p-level value)												
Comparison of drugs (statistical test  ) (p-value)												
Indicator span diagram/ indicator scatter diagram												

 - SNAP-IV subscale score - "inattention."

- SNAP-IV subscale score - "hyperactivity/impulsivity."

- SNAP-IV subscale score - oppositional defiant disorder;

- SNAP-IV subscale score - Conners index;

Clinical Global Impressions-ADHD-Severity scale (CGI-ADHD-S).

- Spence children's anxiety scale (SCAS) scores after 6 weeks of therapy compared to baseline;

PedMIDAS questionnaire score

- ADHD Rating Scale-IV score after 6 weeks of therapy compared with baseline.

 T-test for related samples or Wilcoxon test depending on the type of distribution of the indicator T-test for independent samples or Mann-Whitney test depending on the type of distribution of the indicator**Version 1.0 of 27.9.2019**Protocol-specific version for protocol #PHS-ADHD-002-MEX- TAB,  
version 3.0 dated 19.07.2019.**CONFIDENTIAL**

page 33 of 42

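### The Day 28 telephone ADHD-RS-IV is the only efficacy score scheduled between Day 1 and Day 43, yet no planned analysis uses it

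*Protocol*

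**What the plan says.** The schedule in Protocol 1.2 marks ADHD-RS-IV at Visits 2, 4 and 5. Visit 4 is the telephone contact at Day 28 ± 2, at which the investigator obtains "symptom scores according to the ADHD Rating Scale IV" (Protocol 4.5.5). Footnote 2 to the schedule agrees: "prescribed concomitant medications, ADHD Rating Scale IV score, and remind about adherence to the therapy regimen". The other scales have no mid-treatment assessment: SNAP-IV and CGI-ADHD-S are marked at Visits 1, 2 and 5, SCAS and PedMIDAS at Visits 2 and 5, and CGI-I at Visit 5.

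The ADHD-RS-IV endpoint is "Mean change on ADHD Rating Scale-IV scores after 6 weeks of therapy vs. baseline" (Protocol 7.1). SAP Table 4 lists it as "ADHD Rating Scale-IV score after 6 weeks of therapy compared with baseline". That table has columns for Visit 2, Visit 5 and their change, with arms compared by t-test or Mann-Whitney test. The primary endpoint is "Mean change in the total score on the inattention and hyperactivity/impulsivity subscales of the SNAP-IV scale after 6 weeks of therapy vs. baseline" (Protocol 4.1).

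On missing data:
- The FAS takes treated children "who have an assessment of response to therapy after 6 weeks of therapy" (Protocol 9.7).
- For children with Visit 6 data but none from Visit 5, Protocol 10.2 says "these patients will not be included in the FAS and PP populations".
- Protocol 9.5 rules out replacing missing values.
- SAP section 6 adds, as a sensitivity check on the primary parameter, "analyses of full cases and post-hoc analyses using the last observation carry forward method (LOCF").
- Protocol 5.5 would use drop-outs' data for efficacy where it can, but names no method.
- Protocol 4.5.9 and 5.3 ask early leavers to complete the Visit 5 procedures, which include SNAP-IV and ADHD-RS-IV.

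**The concern.** The trial collects a mid-treatment symptom score and then gives it no role. Neither document specifies a Day 28 summary, a repeated-measures model, or any use of the score for children who miss week 6.

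This matters because of how the plan treats those children. They leave the FAS, and the only check on their absence is complete cases plus LOCF. SNAP-IV has no scheduled value after baseline and before Visit 5. For a child lost without an early-termination examination, LOCF can therefore carry only the baseline, which asserts exactly zero change. The Day 28 score is direct evidence on that assertion. It is also close in content to the primary outcome: the 18 items in Protocol 17.3 closely match SNAP-IV items 1–9 and 11–19 in Protocol 17.1.

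At stake is mainly the credibility of the missing-data analysis, and to a small degree precision.

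**Working it through.** **Inputs from the documents (Protocol 9.2):** difference 2.5 points; SDs 4.70 (placebo) and 7.515 (Mexidol); two-sided alpha 0.05; power 80%; drop-out 10%; 100 completers and 111 randomised per arm.

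**Reproducing the plan's figure.**
- Pooled SD = √[(4.70² + 7.515²)/2] = 6.268 (plan: 6.27).
- n per arm = 2 × 6.268² × (1.960 + 0.842)² / 2.5² = 98.7, so 99. The t-based calculation gives 100, as stated.
- 100/0.90 = 111.1 per arm (plan: 111), and 3 × 111 = 333. 333/0.80 = 416.25, so 417 screened. The plan's numbers hold.

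**Children affected.** 111 − 100 = 11 expected drop-outs per arm, 33 in all.

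**Assumed, because the documents give no figure:** the share f of drop-outs who leave after Day 28 (0.25 to 0.75), and the correlation ρ between Day 28 ADHD-RS-IV and week-6 SNAP-IV (0.3 to 0.8). Then 0.25 × 11 = 2.75 to 0.75 × 11 = 8.25 drop-outs per arm, about 3 to 8, would have a Day 28 score.

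**Approximate value of the score.** Each such child returns about ρ² of a patient, so effective n = 100 + f × 11 × ρ². Power is Φ[2.5/(6.268 × √(2/n)) − 1.960], which is 80.5% at n = 100.

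| f | ρ | Effective n per arm | Power, % |
|---|---|---|---|
| 0.25 | 0.3 | 100.25 | 80.62 |
| 0.25 | 0.5 | 100.69 | 80.79 |
| 0.25 | 0.7 | 101.35 | 81.04 |
| 0.25 | 0.8 | 101.76 | 81.20 |
| 0.50 | 0.3 | 100.50 | 80.72 |
| 0.50 | 0.5 | 101.38 | 81.05 |
| 0.50 | 0.7 | 102.69 | 81.55 |
| 0.50 | 0.8 | 103.52 | 81.85 |
| 0.75 | 0.3 | 100.74 | 80.81 |
| 0.75 | 0.5 | 102.06 | 81.31 |
| 0.75 | 0.7 | 104.04 | 82.04 |
| 0.75 | 0.8 | 105.28 | 82.49 |

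The gain is 0.2 to 5.3 effective patients per arm, or roughly 0.1 to 2.0 points of power. If nobody at all were lost (111 per arm), power would be 84.4%.

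**Effect of the termination examination.** The table credits every drop-out after Day 28. Take f = 0.5 and ρ = 0.7, and suppose half of these 5.5 children attend that examination (an assumption). The gain that only Day 28 can supply falls from 0.49 × 5.5 = 2.7 to 0.49 × 2.75 = 1.3 patients per arm. If all attend, it is near zero.

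**Visit numbers.** In SAP section 11 and Table 2, Visit 4 means Day 43. In SAP Tables 3 and 4, and in protocol 4.0, Day 43 is Visit 5. Under protocol 4.0 numbering Visit 4 is the Day 28 call, so the SAP's population rule, read literally, would make FAS membership depend on that call.

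**The case against.** The strongest objection is the recall period. The printed ADHD-RS-IV form (Protocol 17.3) asks about the last 6 months, and nothing shortens this for the Day 28 call, whereas the headache forms do get an explicit 6-week window. Taking 6 months as about 180 days, only 28/180, or 16%, of the period would be on treatment, so the score might say little beyond baseline. This stands as a limit on the gain. It is not a reason to ignore the score: the Day 43 ADHD-RS-IV, which the plan does analyse, has the same weakness (42/180, or 23%).

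Second, a reader might infer that information on all later drop-outs is thrown away. The documents do not support that. Early leavers are asked for a full Visit 5 examination, if possible within 24 hours of the decision, so some will have a later score on the primary scale itself. The plan does not say whether that score counts as the week-6 assessment or feeds the LOCF. The point about Day 28 is confined to children lost without that examination; loss of contact is a listed withdrawal reason.

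Third, the correlation is assumed, and it crosses two instruments and two modes of contact. What helps imputation is the association left after baseline SNAP-IV is in the model, which may be lower. A single figure such as 2.7 patients per arm is therefore not supportable.

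Finally, the SAP lets methods be supplemented, and it was written for protocol 3.0, so its silence may partly reflect version lag. The score is not barred from analysis; no analysis of it is specified.

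**Conclusion.** The point holds as a minor one. The Day 28 ADHD-RS-IV is scheduled for every child still in the trial and appears in no planned analysis. For a child lost after Day 28 without a termination examination, the plan would impute zero change on SNAP-IV while holding an unused on-treatment score.

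The gain in precision is small: about 0.2 to 5 effective patients per arm, with power moving from 80.5% to 80.6–82.5%. This rests on the assumed ranges for drop-out timing and correlation. It shrinks towards zero if early leavers attend the termination examination or if the 6-month recall blunts the score. The main benefit is a missing-data assumption that is easier to defend than complete cases plus LOCF; the documents do not allow its effect on bias to be quantified.

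A reader might infer that the trial is underpowered for this reason. It is not: the sample size is already based on completers and reproduces.

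**What to change.** 1. Analyse ADHD-RS-IV in all randomised, treated children with one repeated-measures model (baseline, arm, visit, arm × visit; Days 28 and 43), reporting the Day 43 contrast. The FAS as defined will not serve, because it drops the children whose Day 28 score matters.
2. Replace the post-hoc LOCF with a pre-specified multiple-imputation sensitivity analysis of week-6 SNAP-IV in the same children. Use baseline SNAP-IV, Day 28 ADHD-RS-IV and any early-termination scores as predictors.
3. Align the SAP's visit numbers with protocol 4.0, in section 11 and Table 2 above all, so that the population rules refer to Day 43.
4. State the recall period used for ADHD-RS-IV at Day 28 and Day 43.

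The cost is extra programming and a SAP amendment, which the version mismatch already calls for. No new data are needed.
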